## STUDY DESIGN

A type 1 hybrid effectiveness-implementation design will be used in this study. The study will assess the effectiveness of Oculus Quest Virtual Reality (VR) Headset fitted with a smartphone on perioperative anxiety among adults undergoing elective surgery (Aim 1); while the implementation is observed and information gathered on the potential barriers and facilitators to its widespread uptake (Aim 2). This selected type of design is appropriate in order to provide a pathway for the rapid transfer of knowledge from research to implementation if the intervention is effective (Curran, Bauer, Mittman, Pyne, & Stetler, 2012).

## **RESEARCH AIMS**

The aims of this study are:

- 1- To evaluate the effectiveness of using VR technology for perioperative anxiety among adults undergoing elective surgery.
- 2- To identify the potential barriers and facilitators to the widespread implementation of VR for perioperative anxiety

# STUDY SETTING

This study will be conducted in the surgical unit at King Abudulaziz University Hospital, Jeddah city, Western region, Saudi Arabia. The King Abudulaziz University Hospital is the largest tertiary care hospital in the western region. The facilities have the most advanced technology infrastructure, and they are staffed with about 4,000 healthcare providers and administrators (King Abdulaziz University Hospital, 2015). The bed capacity is 1,067. The department of operation room consists of 25 operating rooms distributed as follows; 16 major operating theaters in the main operating rooms (OR); 2 operating theaters in the emergency department; 2 theaters in the labor delivery; 4 theaters for one day surgery; and one burn unit operating room. The OR department is serving most surgical specialties ,including general surgery, neurosurgery, cardiac surgery, thoracic surgery, ophthalmic, ears nose and throat (ENT), plastic, pediatric, vascular ,and robotic surgery (King Abdulaziz University Hospital, 2015).

### 3.1 AIM ONE

Evaluate the effectiveness of using VR technology for perioperative anxiety among adults undergoing elective surgery.

### DESIGN

A two-group parallel Randomised Controlled Trial (RCT) with allocation ratio 1:1 will be conducted in accordance with the CONSORT guidelines (Schulz, Altman, & Moher, 2010); 150 patients undergoing elective surgery will be randomised to the control (standard preoperative care) or the intervention (routine preoperative care with VR) group.

#### **HYPOTHESIS**

Compared with standard care, the VR intervention delivered during the preoperative period will significantly reduce perioperative anxiety in adult elective surgical patients by 20 points on a 100-point Visual analog scale for anxiety (VAS-A).

### RECRUITMENT

The PhD candidate will consult the hospital's admission team, who will review the surgical list and identify potential participants. The potential participants will be asked by the preoperative clinic nurse to take part in the study during their preoperative visit. They will be provided with a participant information statement and consent form. The consent form will have two agreement statements: the first statement regarding participating in the quantitative study, the second statement regarding participating in the quantitative study, the instructed to return their signed consent prior to their day of surgery if they are interested in participating in the study.

### INCLUSION AND EXCLUSION CRITERIA

Patients will be eligible for inclusion if they are 18 years old and over; scheduled for elective surgery; able to understand Arabic and follow instructions. Patients will be excluded if they scheduled to undergoing dental surgery; have mental illness; visual or hearing problems; history of seizures or motion sickness; an inability to complete a self-reported questionnaire, or cognitive impairment.

### SECREEING

Patients who meet the above inclusion criteria will be screened for their anxiety level using a validated tool which is The Amsterdam Preoperative Anxiety and Information score (APAIS) (Boker et al., 2002; Laufenberg-Feldmann & Kappis, 2013). The PhD candidate will apply the Amsterdam Preoperative Anxiety and Information score (APAIS) on the day of their surgery in the preoperative holding area. Patients with moderate to high level of preoperative anxiety - defined as a preoperative anxiety score ≥11 (Song et al., 2019) - will be included.

The APAIS is a rapid and clinically practical assessment tool developed by Nelly Moerman and previously validated against other scales to evaluate patients' preoperative anxiety with good sensitivity and strong specificity for clinically significant anxiety (Boker et al., 2002; Laufenberg-Feldmann & Kappis, 2013). It consists of six questions in total. Each question is rated on a five-point Likert scale from 1: "not at all" to 5: "extremely". The sum of scores from questions 1, 2, 4, and 5

show the anxiety level. The sum of scores from questions 3 and 6 show the level of information required by each individual regarding the anesthesia and surgical procedure. A patient with a score of 11 or more (scoring range from 4 to 20) on the anxiety scale experiences moderate to severe anxiety requiring further intervention (Berth, Petrowski, & Balck, 2007; Boker et al., 2002; Laufenberg-Feldmann & Kappis, 2013). On the need for information scale, patients scoring 2 – 4 are categorised as having little and no need for information, patients scoring 5 – 7 are categorised as having an average need for information and the patients scoring 8 – 10 are considered as having high need for information(Berth et al., 2007; Laufenberg-Feldmann & Kappis, 2013).

Amsterdam Preoperative Anxiety and Information score (APAIS)(Berth et al., 2007):

Questions:	1	2	3	4	5
1- I am worried about the anesthetic					
2- The anesthetic is on my mind continually					
3-I would like to know as much as possible about the anesthetic					
4- I am worried about the procedure					
5-The procedure is on my mind continually					
6- I would like to know as much as possible about the procedure					

1:Not at all, .2:Somewhat, 3:Moderate, 4: Moderately high, 5:Extremely

### RANDOMISATION

Participants will be randomly allocated to intervention or control via block randomisation on a 1:1 ratio (control: intervention) using a computerised random number sequence created by an independent statistician. In addition, randomisation will be stratified by surgery type (i.e., general surgery, neurosurgery, cardiac surgery, thoracic surgery, and orthopedic surgery).

### ALLOCATION CONCEALMENT

Sealed opaque envelopes organised in numbered sequential order will be used to conceal the treatment allocation. Following screening, potential participants with moderate to high levels of

anxiety will be allocated to the treatment group (either intervention or control) contained in the next envelope.

### INTERVENTION AND CONTROL

The control group will receive standard preoperative care only, while the intervention group will receive standard preoperative care plus VR. Standard preoperative care will include the preparation of the preoperative surgical site, preoperative bathing, preoperative hair removal, wearing theater gown, remove all jewelry, correct patient ID bracelet, and complete patient preoperative checklist and health record.

### VIRTUAL REALITY INTERVENTION

[figure not shown]
The participants will be given VR for 5 to 10 minutes, which has been suggested in the literature to be an effective time frame to apply VR without adverse side effects (Chow et al., 2016; Lawson, 2014). Exposure to VR should not last longer than 30 minutes to avoid VR adverse effects (Lawson, 2014). Sickness in virtual environments has been found to increase after ten minutes with head-mounted displays in simulator studies (Min, Chung, Min, & Sakamoto, 2004; Moss et al., 2011). The potential participants will be seated in a quiet environment and will be watching a natural scene with natural sound in the preoperative holding area. This area has been selected because evidence suggests that preoperative anxiety levels among adult surgical patients peaks in the preoperative holding area (Pokharel, Bhattarai, Tripathi, Khatiwada, & Subedi, 2011). The participant's face and forehead will be cleaned using skin-friendly antibacterial cleaning wipes before using the VR device. Disposable Hygiene Covers will also be used to protect the VR device.

# **PRIMARY OUTCOME**

Perioperative anxiety as measured by the visual analog scale for anxiety (VAS-A).

The visual analog scale for anxiety (VAS-A) is valid, reliable, and frequently used for evaluation of perioperative anxiety that allows detection of high anxiety levels in the various surgical group

(Kindler, Harms, Amsler, Ihde-Scholl, & Scheidegger, 2000). The VAS-A consists of a 100 mm horizontal line that represents two behavioral extremes at either end of the continuum (i.e., 'not at all anxious' = 0, whereas 'extremely anxious' = 100). Potential participants will be asked to rate their level of anxiety on the VAS-A tool at three-time points in the study. On admission to the preoperative area (T1), immediately before surgery (T2), and one hour after surgery (T3). Scores on the VAS-A of 25 or higher are said to reflect significant levels of anxiety (Kindler et al., 2000). The primary outcome will be collected by a Research Assistant at the research site, King Abdulaziz University Hospital.

## Visual analog scale for anxiety (VAS-A)

### SECONDARY OUTCOMES

1. Stress level as measured by:

A) Cortisol levels measured using Salivette® Cortisol.

Saliva cortisol levels are widely used as a biomarker for psychological stress and associated mental or physical diseases (Hellhammer, Wüst, & Kudielka, 2009; Reinhardt, Schmahl, Wüst, & Bohus, 2012). The Salivette® Cortisol is specially designed to achieve reliable analytical values from small volumes and very low cortisol samples (Sarested AG &Co). Saliva samples will be collected from participants at three-time points; on admission to the preoperative area (**T1**) and immediately before surgery (**T2**) and one hour after surgery (**T3**). The samples will be collected by a Research Assistant at the research

Study Protocol

site, King Abdulaziz University Hospital. The Samples will be collected, labelled, and sent to pathology by a researcher.

B) Heart rate (HR) as measured using Polar continuing heart rate sensor.

Increase HR is considered a physiological reaction to stressful situations. This reaction occurs as a result of the fight-or-flight response to a stressful situation, which is controlled by the autonomic nervous system (Gilbert & Gilbert, 2003). The participants will wear the Polar sensor (Figure 2) on their arm, and the HR will be analysed at three-time points. On admission to the preoperative area (T1), immediately before surgery (T2) and one hour after surgery (T3). The HR will be measured by a Research Assistant at the research site, King Abdulaziz University Hospital.

2- Postoperative pain as measured by the visual analog scale for pain (VAS-P).

The visual analog scale for pain (VAS-P) is valid, reliable and commonly used to measure subjective pain (Hawker, Mian, Kendzerska, & French, 2011). The VAS-P consists of a 100 mm horizontal line that represents two behavioral extremes at either end of the continuum (i.e., 'no pain' = 0, whereas 'worst pain' = 100). The participants will be asked to rate their pain on the VAS-P tool at two-time points; on admission to the preoperative area (T1), and one hour after surgery (T3). This outcome will be collected by a research assistant at the research site, King Abdulaziz University Hospital.

**3- Patient satisfaction** as measured by the Leiden Perioperative Patient Satisfaction questionnaire (LPPSq).

The Leiden Perioperative Patient Satisfaction questionnaire (LPPSq) is a valid and reliable tool used to assess and measure different aspects of patient satisfaction with perioperative care (Caljouw, Van Beuzekom, & Boer, 2008). This questionnaire consists of 39 questions which are divided over six dimensions; (1) information provision (four questions), (2) discomfort and needs (seven questions), (3) fear and concern (seven questions), (4) professional competence (four questions), (5) staff -patient relationship (14 questions), and (6) service quality (three questions). Patient satisfaction with

Study Protocol

perioperative care will be expressed by the mean satisfaction scores and the percentage of the maximum possible scores for each dimension (Caljouw et al., 2008). The participants will be asked to complete the questionnaire 24 hours after surgery before they are discharged (T4). This outcome will be collected by a research assistant at the research site, King Abdulaziz University Hospital.

4- Hospital Length of Stay (LOS) as measured from the date of admission to discharge from hospital.

The hospital length of stay is a proven recovery time indicator that can be used as a valid measure of robust outcomes in a variety of surgical fields and medical conditions (Laderman & Mate, 2016). The LOS will be measured in days that recorded on patients' discharge summary by subtracting the date of admission to hospital from the date of discharge from hospital (Abdelhak, Grostick, & Hanken, 2014). This outcome will be collected by a research assistant at the research site, King Abdulaziz University Hospital.

5- Adverse effect of VR intervention at any time point as measured by the Virtual Reality Symptom Questionnaire (VRSQ)

The Virtual Reality Symptom Questionnaire (VRSQ) is a valid and reliable measure used to evaluate the possible occurrence of symptoms of cybersickness, a type of motion sickness caused by exposure to VR (Sevinc & Berkman, 2020). This questionnaire assesses eight general physical side effects, (1) general discomfort, (2) fatigue, (3) boredom, (4) drowsiness, (5) headache, (6) dizziness, (7) concentration difficulties, and (8) nausea. It also assesses five visual effects (1) tired eyes, (2) aching eyes, (3) eyestrain, (4) blurred vision, and (5) difficulties focusing on a seven-point range from 0 to 6, with 0 indicating that the symptom is not present and 6 that the symptom is severe. The potential participants in the intervention group will be asked to complete the questionnaire immediately before surgery (T2). This outcome will be collected by the PhD candidate.

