# Summary of Outcomes variables and Measures:

Variable	Scales/Questionnaires/instruments
Primary outcome	
Perioperative anxiety	Visual Analog Scale for Anxiety (VAS-A)
Secondary outcomes	
1. Stress level	Saliva cortisol test
	Mean Heart rate
2. Postoperative pain	Visual Analog Scale for pain (VAS-P)
3. Patient satisfaction	Leiden Perioperative Patient Satisfaction Questionnaire (LPPSQ)
4. Hospital Length of Stay (LOS)	Date of admission to the hospital from the date of discharge
5. Adverse effect of VR intervention	The Virtual Reality Symptom Questionnaire (VRSQ)

	S	TUDY P	PERIOD					
	Pre-admission	Preo	perative	ohase	Postoperative phase		Discharge	
TIMEPOINT**	-t 1	t o	t 1	t 2	t 3	t4	t 5	
ENROLMENT:								
Eligibility	х							
Informed consent	Х							
screen: using APAIS		Х						
Allocation		Х						
INTERVENTIONS:								
VR exposure				х				
ASSESSMENTS:								
Primary outcome:			x	Х	x			
Perioperative anxiety								
Secondary outcomes:			x	Х	x			
Stress level								
Postoperative pain			х		x			
Patient satisfaction						Х		
Length of hospital stay							X	
Virtual reality adverse effect				Х				

\*\*- $t_1$ : pre-admission; t0: on admission; t1: on admission to preoperative area; t2: immediately before surgery (holding area); t3: one-hour post-surgery; t4: after 24 hours post-surgery and before discharge; t5: discharge.

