# OTHER DATA

Participant's socio-demographic data and surgery data will be collected, including age, gender, marital status, education level, occupation, and type of surgery, type and dose of anaesthetic and previous surgeries. This data will be collected from the participant's health record by the PhD candidate.

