# SAMPLE SIZE

Based on the previous study of Bekelis et al. (2017), a sample of 150 participants (75 per group) will give the study 80% power to detect a moderate effect size of 0.5 standard deviations between groups in the primary outcome variable, with a type 1 error rate of 5%. This calculation assumes a dropout rate of 15%.

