# STATISTICAL PLAN

Characteristics of groups will be summarised using counts and percentages for categorical variables and means and standard deviations for continuous variables. The primary outcome will be compared between groups at each follow-up time points using a linear mixed effects regression model, with fixed effects including treatment arm time (categorical), the interaction between treatment and time, and the baseline value of the outcome variable. Differences in mean VAS anxiety scores

between groups at each time point will be presented together with 95% confidence intervals and pvalue. Continuous secondary outcomes with repeated measurements will be compared using the same model. Hospital length of stay will be compared using the rank-sum test. Patient satisfaction and the VRSQ will be compared between groups using an independent sample t-test.

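### Saliva samples follow surgical events and the cortisol model has no time-of-day term, so part of the daily rhythm stays in the error: a small loss of precision, mostly at T3

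*Protocol*

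**What the plan says.** Under Secondary Outcomes, the protocol fixes the cortisol schedule by event: "Saliva samples will be collected from participants at three-time points; on admission to the preoperative area" (T1), immediately before surgery (T2) and one hour after it (T3). The footnote to the schedule in the Summary of Outcomes repeats this: "t1: on admission to preoperative area; t2: immediately before surgery (holding area); t3: one-hour post-surgery". Neither place sets a clock window.

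The Statistical Plan specifies a linear mixed model for the primary outcome, with arm, categorical time, "the interaction between treatment and time, and the baseline value of the outcome variable" as fixed effects. It then states: "Continuous secondary outcomes with repeated measurements will be compared using the same model". Cortisol therefore gets arm, visit, arm by visit and the T1 cortisol value. Time in this model is the visit, not the hour of the day.

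The Other Data section lists demographic items and "type of surgery, type and dose of anaesthetic and previous surgeries". It does not name the clock time of a sample or of surgery. Secondary Outcomes says the samples will be labelled but not what the label carries.

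**The concern.** Salivary cortisol is generally taken to fall through the day. The protocol does not say so; this is an assumption. A patient's place on the operating list decides when T1, T2 and T3 occur, so two patients' samples for the same visit may be hours apart on the clock. A model written for a self-rated scale is carried over to a hormone assay without a term for this source of variation.

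The T1 cortisol value is an indirect adjustment, because a patient sampled late tends to have a low T1. But it is one noisy sample, so it corrects only in part. At T3, surgery of varying length has also come between the two samples, and T1 carries no information about that length.

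What is at stake is a somewhat wider confidence interval for cortisol, which is one of two measures of the stress outcome beside heart rate. The point matters at protocol stage because a sample time that was never written down cannot be supplied later by an analysis plan.

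**Working it through.** **Inputs from the protocol.** Event-based sampling; the fixed effects above; 1:1 blocked randomisation stratified by surgery type; 150 patients with 15% dropout. The protocol gives no cortisol SD, rhythm, spread of start times or surgery duration.

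**Step 1: the plan's own figure.** Sample Size says "a sample of 150 participants (75 per group) will give the study 80% power to detect a moderate effect size of 0.5 standard deviations". Taking the 5% error rate as two-sided, n per arm = 2 × (1.960 + 0.842)² / 0.5² = 62.8, so 63. With dropout, 63 / 0.85 = 74.1, so 75 per arm and 150 in total. The figure reproduces, but it concerns the anxiety score only. About 150 × 0.85 = 127.5, say 128, patients would be evaluable.

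**Step 2: T2, closed form.** Assumptions: log-cortisol falls linearly with clock time; T1 times are uniform over the stated spread; T2 follows T1 at a nearly constant interval; between-person SD is 0.3 or 0.4 (variance B = 0.09 or 0.16); sample noise SD is 0.4 (variance E = 0.16).

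- Clock variance: C = slope² × spread² / 12. Total variance: S = C + B + E.
- Residual variance given T1 cortisol: R1 = S − (C + B)² / S.
- Residual variance given T1 cortisol and T1 clock time: R2 = (B + E) − B² / (B + E), which is 0.2176 for B = 0.09 and 0.2400 for B = 0.16.
- Variance saved: 1 − R2 / R1.
- Share of clock variance left in the error when only T1 cortisol is in the model: (E / S)².

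Example with slope 0.10, spread 8 h and B = 0.09: C = 0.01 × 64 / 12 = 0.0533; S = 0.3033; R1 = 0.3033 − 0.1433² / 0.3033 = 0.2356; saving = 1 − 0.2176 / 0.2356 = 7.6%; share left = (0.16 / 0.3033)² = 28%.

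| Slope per h, spread | C | R1 (B = 0.09 / 0.16) | Saved | Clock variance left |
|---|---|---|---|---|
| 0.05, 3 h | 0.0019 | 0.2184 / 0.2405 | 0.3% / 0.2% | 40% / 25% |
| 0.10, 6 h | 0.0300 | 0.2286 / 0.2469 | 4.8% / 2.8% | 33% / 21% |
| 0.10, 8 h | 0.0533 | 0.2356 / 0.2514 | 7.6% / 4.5% | 28% / 18% |
| 0.15, 8 h | 0.1200 | 0.2508 / 0.2618 | 13.2% / 8.3% | 19% / 13% |

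**Step 3: cost of the extra term.** One covariate at n = 128 costs about 1 / 125 = 0.8% of variance. Simulation at that size (300 replicates per setting) agrees. The net saving at T2 is about −0.5% for slope 0.05 over 3 h, 1.7% to 4.1% for 0.10 over 6 h, 4.0% to 7.3% for 0.10 over 8 h, and 7.2% to 12.8% for 0.15 over 8 h. On the raw scale the results are similar, up to 10.3%.

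**Step 4: T3.** A second simulation (400,000 records) assumed T1 between 07:00 and 14:00, T2 0.5 to 1 h later, surgery lasting 1 to 6 h, slope 0.06 to 0.12, and between-person/noise SDs of 0.4/0.4 or 0.5/0.3. With T1 cortisol in the model, 6% to 23% of the clock variance remained at T2 and 37% to 49% at T3. Leaving out the clock times of both T1 and the follow-up sample raised the standard error by 0.3% to 2.6% at T2 and by 2% to 10% at T3.

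Most of that T3 loss is beyond the reach of T1 clock time. At slope 0.12 with SDs 0.4/0.4, T1 and T3 clock times together lower the residual variance from 0.281 to 0.239, a drop of 0.042. Surgery length alone contributes 0.12² × 5² / 12 = 0.030 of this. About 0.012 is left for T1 clock time, or 0.012 / 0.281 = 4%.

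**Step 5: what a saving is worth.** For a comparison with 80% power, a 2% saving moves 2.802 to 2.802 / √0.98 = 2.830, which gives 81% power. An 8% saving gives 2.802 / √0.92 = 2.921, or 83%.

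**The case against.** The strongest reply is that nothing here is invalid. The model gives an unbiased arm comparison, it already adjusts for each patient's own same-day cortisol, and a further prognostic covariate is the kind of detail an analysis plan may add. That plan is not shown and may contain the term. The Other Data list is introduced as non-exhaustive, and the label contents are not described, so silence does not prove that sample times go unrecorded. All of this stands and limits the point to an improvement. What survives is that the protocol does name a model for cortisol, and that nothing in it commits the team to recording a time that cannot be recovered afterwards.

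A second reply is that the size rests wholly on assumptions and includes no gain. That also stands.

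A third is that the schedule puts allocation at t0, before T1, so T1 clock time is not strictly a pre-allocation variable. The Screening and Allocation Concealment sections leave the order less clear. In practice the operating list sets this time, clinicians are not to be told the allocation, and T1 precedes VR, so the risk from adjusting for it is slight.

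Stronger readings are tempting. A reader might infer that the arms are compared at different hours and the cortisol result is biased; randomisation balances clock time in expectation, so the documents do not support that. A reader might infer that the whole rhythm sits in the error term; the T1 covariate rules that out. A reader might credit the whole T3 loss to the missing T1 clock time; most of it comes from surgery length.

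**Conclusion.** The point holds as a minor one. Event-based sampling with no time-of-day term leaves part of any daily cortisol rhythm in the error: the smaller part at T2, and a larger part at T3. The consequence is a small loss of precision on one secondary outcome for which the protocol claims no power; the validity of the comparison is not affected.

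Adding T1 clock time would lower the variance of the T2 arm difference by about 2% to 8% in middle cases and up to about 13% with the steepest slope and the widest spread. With a short operating list or a flat rhythm the gain is nil, or a loss of under 1%. These figures depend on the assumed slope, spread and SDs, none of which is in the protocol, so confidence in the size is low. Confidence in the direction depends only on there being a rhythm and a spread of sampling times.

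**What to change.** Record the clock time of each saliva sample on its label, and state this under Secondary Outcomes. In the Statistical Plan, add the clock time of the T1 sample as a fixed covariate to the cortisol model. Use T2 and T3 clock times only in a sensitivity analysis, because they arise after VR and could in principle be affected by it. That analysis can show how much of the T3 variation is due to surgery length, which the T1 term cannot reach.

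The cost is one field on a label that is already being written and one degree of freedom. If surgery starts fall within a narrow window, the term gains nothing.

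### Length of stay starts at hospital admission, while allocation and VR fall on the day of surgery; any varying pre-operative stay adds noise, but no bias, to this secondary outcome

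*Protocol*

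**What the plan says.** The Secondary Outcomes section of the protocol lists "Hospital Length of Stay (LOS) as measured from the date of admission to discharge from hospital", calculated in days "by subtracting the date of admission to hospital from the date of discharge from hospital". The summary table of outcomes uses the same two dates. The reason given for the outcome is that "The hospital length of stay is a proven recovery time indicator".

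The Screening section has the anxiety screen (APAIS) applied "on the day of their surgery in the preoperative holding area". The Allocation Concealment section opens the next envelope after that screen: "Following screening, potential participants with moderate to high levels of" anxiety are then allocated. The Virtual Reality Intervention section gives VR in the preoperative holding area.

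The schedule table differs on one point. It marks the APAIS screen and allocation at t0 and VR at t2, with the key "t0: on admission; t1: on admission to preoperative area; t2: immediately before surgery (holding area".

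The Statistical Plan compares length of stay by a rank-sum test and names no adjustment. No section says how long before surgery patients are admitted.

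**The concern.** The outcome is meant to show recovery, but its clock starts at hospital admission. On the Screening and Allocation Concealment sections, any night in hospital before the day of surgery comes before randomisation and before VR. Such a night is not recovery from the operation and cannot respond to the intervention, yet it counts.

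If patients differ in how long they wait in hospital before surgery, this variation is added to the outcome in both arms. A real difference in post-operative stay would then be harder to detect. What is at stake is the precision of this one secondary comparison, and how well the number matches its stated purpose.

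**Working it through.** **1. The plan's own figure.** The Sample Size section gives 150 participants for 80% power at 0.5 SD, 5% type 1 error and 15% dropout. Taking the test as two-sided:

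- n per arm = 2 × (1.960 + 0.842)² / 0.5² = 62.8, rounded up to 63
- with dropout: 63 / 0.85 = 74.1, rounded up to 75 per arm, 150 in total

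The figure reproduces. It concerns VAS-A only; the protocol states no power for length of stay. The number to use for analysed patients is therefore 63 per arm.

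**2. Which time can VR affect?**

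Total stay = (surgery date − admission date) + (discharge date − surgery date).

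Only the second term can respond to VR. Call the first P (pre-operative days) and the second R (post-operative days).

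- Expected difference between arms in total stay = difference in R + difference in P. Randomisation makes the expected difference in P zero, so the difference in days is unbiased.
- Variance of total stay = Var(R) + Var(P), if P and R are independent. The standardised effect therefore falls from d to d / √(1 + r²), where r = SD(P) / SD(R).
- If P is the same for everyone, Var(P) = 0 and nothing is lost.

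For illustration, take d = 0.5 for post-operative stay, 63 per arm, and the normal approximation:

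| r | Standardised effect | Power |
|---|---|---|
| 0 | 0.500 | 80% |
| 0.25 | 0.485 | 78% |
| 0.5 | 0.447 | 71% |
| 0.75 | 0.400 | 61% |
| 1 | 0.354 | 51% |

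**3. The planned test.** The table below is a simulation of the rank-sum test at 63 per arm. None of its length-of-stay inputs is in the protocol; all are assumptions:

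- post-operative stay in whole days, rounded from lognormal(1.2, 0.6) in control and lognormal(0.92, 0.6) with VR
- medians before rounding e^1.2 = 3.3 and e^0.92 = 2.5 days, ratio e^−0.28 = 0.76, so 24% shorter with VR
- pre-operative days independent of post-operative stay, with the same distribution in both arms

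| Pre-operative days | Power |
|---|---|
| None, or the same for everyone | about 70% |
| Half the patients 0, half 1 | 65% |
| Uniform on 0 to 3 | 54% |
| Geometric from 0, mean 1.5 | 45% |

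The mean difference stayed near 0.97 day in every row, as step 2 predicts.

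**4. A second set of assumptions.** With post-operative stay lognormal (median 4 days, log-scale SD 0.5), 20% shorter with VR, and 63 per arm, power was 67% with no pre-operative days and 67% with exactly one day for everyone. It was 63% with half at 0 and half at 1, 50% for uniform 0 to 3, 46% for Poisson with mean 2, and 27% for geometric with mean 3. The mean difference stayed at about 0.9 day throughout. The pattern is the same.

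**5. The timing of allocation.** The text puts screening on the day of surgery and allocation after it. The schedule puts both at t0, on admission, as a time point separate from arrival in the preoperative area. If both are right, admission is on the day of surgery, and the two ways of counting give the same whole-day result. If the schedule alone is right and admission can be earlier, pre-operative nights follow allocation but still come before VR at t2. In either case the passages need to be reconciled.

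**The case against.** The strongest reply is that pre-operative nights are not shown to exist. Patients are "scheduled for elective surgery", attend a preoperative clinic and return consent before the day of surgery. The hospital has four one-day-surgery theatres, and the schedule's t0 fits same-day admission. This stands: the loss may be zero. But nothing limits entry to same-day admission, and the randomisation strata include cardiac, thoracic and neurosurgery, so the protocol does not exclude earlier admission either.

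A reader might infer that the definition biases the comparison or shrinks the difference in days. The documents do not support that. The definition applies equally to both arms, and randomisation balances pre-operative stay in expectation. Only precision is affected.

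A reader might also take the bottom row of the main table as the expected loss. That row assumes a pre-operative stay with SD √0.6 / 0.4 = 1.9 days, in which 0.6³ = 22% of patients wait three days or more. Nothing in the protocol supports this for elective patients. With half at 0 and half at 1 day, the loss is about 5 points.

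Finally, admission to discharge is the ordinary meaning of hospital length of stay, and the protocol defines it clearly and consistently. That is so, and it is a reason to keep reporting total stay. It does not make time before an operation a measure of recovery from it.

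**Conclusion.** The point holds in a limited form. The definition of length of stay does not match its stated purpose as a recovery measure, because it can include nights before allocation and VR. If pre-operative stay varies between patients, the rank-sum test loses precision. Under the assumptions in the main table, power runs from about 70% (no loss) to 45%; the actual loss depends on an admission-to-surgery interval that the protocol does not give. There is no bias, and no effect on the type 1 error rate, the primary outcome or the sample size of 150. The point is minor, because length of stay is one of five secondary outcomes and the trial is not powered for it.

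**What to change.** Define the outcome as discharge date minus surgery date, and call it post-operative length of stay. Report admission-to-discharge stay descriptively by arm. Change the Secondary Outcomes text and the outcomes summary table together. Reconcile the schedule's placing of screening and allocation at t0 with the Screening and Allocation Concealment sections. If all patients are in fact admitted on the day of surgery, a sentence saying so would settle the length-of-stay point.

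The change needs no new data. Screening takes place on the day of surgery and the post-operative assessments are timed from surgery, so the surgery date is known for every participant. The cost is slightly less comparability with studies that report total stay, which the descriptive figure largely restores.
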